2.1.4.7 Electrocardiogram variables

12-lead ECG assessments will be described as normal or abnormal.

2.1.4.8 Immunogenicity variables

Anti-drug antibodies (ADA) against isatuximab and REGN2810 will be collected according to the pharmacokinetics/pharmacodynamics (PK/PD) flowcharts in Section 1.5 of the protocol.

ADA attributes

Pre-existing ADA is defined as ADA reactive with the biotherapeutic present in subjects before treatment (or before initiation of the clinical study).

Treatment boosted ADA is defined as pre-existing ADAs that were boosted to a higher level following administration of biotherapeutic (ie, any time after the initial drug administration) the ADA titer is significantly higher than the baseline titer. A low serial dilution schema (2-fold or 3 fold) should be applied during titration. A difference in titer values of two titer steps between treatment or follow-up sample and its baseline sample is considered significant. For examples, at least a 4-fold increase in titers for 2- fold serial dilution schema (or 9-fold increase in titers for 3- fold serial dilution schema). If no titer could be determined for a positive sample, the titer will be reported as the minimal required dilution of the assay.

Treatment-induced ADA is defined as ADAs developed *de novo* (seroconversion) following administration of the biotherapeutic (i.e., formation of ADAs any time after the initial drug administration in a subject without pre-existing ADAs). If the baseline ADA sample is missing or non-reportable and at least one reportable ADA sample is available during the treatment (including follow-up period) the baseline sample will be considered as “negative” for data analysis. This is considered being a conservative approach for ADA assessment.

Subject status

Among evaluable population for immunogenicity (described in [Section 2.3.5](#)), following patient status will be defined:

- **ADA-positive** subject: A subject with at least one treatment induced or treatment boosted ADA-positive sample at any time during the treatment or follow-up observation period
- **ADA-negative** subject: Subject without any treatment induced or treatment boosted ADA-positive sample during the treatment or follow-up observation period
- **ADA-inconclusive** subject: A subject who cannot irrefutably be classified as ADA negative (eg, all post baseline samples inconclusive)

Overview of the ADA response

Two main categories can be reported for the epidemiology of an ADA immune response: ADA prevalence and ADA incidence:

- **ADA prevalence** defines the proportion of all subjects tested positive for ADAs (including preexisting antibodies, treatment boosted ADAs and treatment induced ADAs) at any point in time
- In contrast the term **ADA incidence** only defines the proportion of subjects found to either have seroconverted (treatment induced ADAs) or boosted their pre-existing ADA response during the study. Only evaluable subjects (described in [Section 2.3.5](#)) are considered for computing ADA incidence

Kinetics of the immune response

- **Onset of ADA:** refers to the time period between the initial drug administration and the first instance of treatment induced ADAs. The use of real-elapsed days should be used for the calculations. The “median time to ADA development” and the quartiles Q1 and Q3 should be reported
- **Duration of ADA:** ADA duration will be calculated as the date of last treatment induced ADA sample minus date of first treatment induced or treatment boosted ADA sample +1; ADA duration will be calculated only for patients with at least two ADA positive samples. Median duration of an induced ADA response and the quartiles Q1 and Q3 should be reported
- **Transient ADA response** is defined by:
 - Treatment induced ADA detected only at one sampling time point during the treatment or follow-up observation period (excluding the last sampling time point), OR

- Treatment induced ADA detected at two or more sampling time points during the treatment (including follow-up period if any), where the first and last ADA-positive samples (irrespective of any negative samples in between) are separated by a period less than 16 weeks, and the patient's last sampling time point is ADA negative
- **Persistent ADA response** is defined by:
 - Treatment induced ADA detected at two or more sampling time points during the treatment (including follow-up period if any), where the first and last ADA-positive samples are separated by at least 16 weeks (irrespective of any negative samples in between)
- **Indeterminate ADA** is defined by:
 - Treatment induced ADA detected only at the last sampling time point, OR
 - The last two samples being ADA-positive and separated by a period of less than 16 weeks

Treatment-boosted ADAs are excluded from the analysis of ADA kinetics.

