- m During the treatment phase, the ADA samples for REGN2810 must be collected before REGN2810 treatment administration at each time point: Cycle 1 Day1, Cycle 1 Day 22 (predose Cycle 2), and on Day 1 every 3 cycles afterwards (ie, Cycle 5, Cycle 8, Cycle 11, Cycle 14 etc). In response to AEs of special interest, such as anaphylaxis or hypersensitivity, ADA samples closer to the event may be collected, based on the judgment of the Investigator and/or medical monitor. For the patients with NSCLC who are enrolled for Phase 2 Stage 1 after implementation of Amendment #5 at individual sites, no REGN2810 ADA samples will be collected.
- n During the posttreatment follow-up period REGN2810 ADA samples are collected at 90 ±7 days after last study treatment and every 3 months thereafter until the sample is negative (ASF01, ASF02...).

Amended Clinical Trial Protocol No. 05 SAR650984-ACT15319 - isatuximab

- o During the treatment phase, the ADA samples for isatuximab must be collected before isatuximab treatment administration on Day 1 of each Cycle (could be drawn at the same time just before REGN2810 administration). ADA samples are not collected at Cycle 1 Day 8 or Cycle 1 Day 15. For the patients with NSCLC who are enrolled for Phase 2 Stage 1 after implementation of Amendment #5 at individual sites, no isatuximab ADA samples will be collected.
- p During the posttreatment follow-up period isatuximab ADA samples are collected at 90 ±7 days after last study treatment and every 3 months thereafter until the sample is negative (APF01, APF02...).

  Abbreviations: AB=antibody; ADA=anti-drug antibody; AP=antibody plasma (for isatuximab); AS=antibody serum (for REGN2810); EOI=end of IV infusion; IMP=investigational medicinal product; P=Plasma; PD=pharmacodynamics; PK=pharmacokinetics; RNT=relative nominal time; S=Serum; SOI=start of IV infusion.

11-Jun-2019 Version number: 1

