2.4.6.7 Analysis of Immunogenicity

Immunogenicity analysis will be done separately for isatuximab and REGN2810.

Number of evaluable patients, number (%) of pre-existing ADA and negative patients at baseline, number (%) of boosted and induced patients (either transient, persistent or indeterminate) will be reported, along with descriptive statistics of titer, by cohort and possibly overall. Prevalence and incidence will also be presented.

In addition, for positive ADA patients, time to onset, duration of ADA response, and the characterization of the immune response (transient, persistent, indeterminate) will be provided.

An individual data listing with ADA samples status (positive, negative or inconclusive), the titer if applicable, date of first/last dose, duration of exposure, study period, cycle/day, time point and date/time of sampling along with C_{trough} value of the drug will be provided for all patients.

The impact on safety and efficacy endpoints may be further explored by graphical methods or descriptively, depending on the ADA prevalence.

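### The SAP's persistent and indeterminate ADA classes use different intervals, so a patient still positive at the last sample can fall in two classes or in none

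*SAP*

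**What the plan says.** SAP 2.1.4.8 sorts treatment-induced ADA into three classes.

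- **Transient**, one positive: "Treatment induced ADA detected only at one sampling time point during the treatment or follow-up observation period (excluding the last sampling time point"). With two or more positives, the first and last must be "separated by a period less than 16 weeks, and the patient's last sampling time point is ADA negative".
- **Persistent**: two or more positives, "where the first and last ADA-positive samples are separated by at least 16 weeks (irrespective of any negative samples in between"). Nothing is required of the last sample.
- **Indeterminate** has two limbs. The first is a lone positive result at the patient's final sample. The second reads "The last two samples being ADA-positive and separated by a period of less than 16 weeks", and it requires nothing of earlier samples.

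Boosted responses are set aside: "Treatment-boosted ADAs are excluded from the analysis of ADA kinetics". No order of precedence among the classes is stated.

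SAP 2.4.6.7 splits induced patients into these three classes for each drug, and for ADA-positive patients "the characterization of the immune response (transient, persistent, indeterminate) will be provided".

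Protocol 1.5.1 sets the sampling. Isatuximab ADA is drawn on Day 1 of every 21-day cycle. REGN2810 ADA is drawn at Cycles 1, 2, 5, 8, 11 and so on. After treatment, "isatuximab ADA samples are collected at 90 ±7 days after last study treatment and every 3 months thereafter until the sample is negative"; the REGN2810 rule is the same. A footnote also ends isatuximab ADA collection at follow-up or at the cut-off date, whichever is first.

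**The concern.** Persistent is judged on the time from first to last positive sample. The second limb of indeterminate is judged on the time between the last two samples. Where planned samples are always closer than 16 weeks, that limb is met by anyone positive at the last two samples, however long the response has lasted. A patient positive at every visit for a year would meet both definitions.

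The rules also leave a hole. Take isatuximab positive at Cycle 3, negative at Cycle 4 and positive at Cycle 5, with Cycle 5 the last sample. This is not transient (last sample positive), not persistent (span 6 weeks) and not indeterminate (two positives, but not at the last two samples).

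The immunogenicity of both drugs is a secondary objective, and the planned table presumes classes that are exclusive and complete. As written, they need not sum to the number of induced patients, and the programmer has to invent a rule.

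**Working it through.** The plan gives no figure to reproduce. The check applies the definitions literally, with 16 weeks = 112 days.

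**Step 1. Planned gaps between consecutive ADA samples (Protocol 1.5.1)**

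| Drug and period | Gap in days | Under 112? |
|---|---|---|
| Isatuximab, on treatment | 21 | yes |
| Isatuximab, last dose to 90-day sample | 90 ± 7 = 83 to 97 | yes |
| Isatuximab, 3-monthly repeats | about 91 | yes |
| REGN2810, on treatment after Cycle 2 | 3 × 21 = 63 | yes |
| REGN2810 to 90-day sample, last dose at a sampling cycle | 83 to 97 | yes |
| Same, last dose one cycle later (e.g. Cycle 6) | 21 + 90 = 111; window 104 to 118 | depends on the visit |
| Same, last dose two cycles later (e.g. Cycle 7) | 42 + 90 = 132; window 125 to 139 | no |

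The gap condition therefore never discriminates for isatuximab on schedule. For REGN2810 it sometimes does, at the 90-day sample.

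**Step 2. Isatuximab sampled at Cycles 2 to 8 and cut off on treatment**

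Samples fall on days 21, 42, 63, 84, 105, 126 and 147, giving 2^7 − 1 = 127 patterns with at least one positive.

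- Last sample negative: 2^6 − 1 = 63. The longest span is 126 − 21 = 105 days, so all are transient only.
- Persistent needs a span of 112 days. Only day 21 to day 147 (126 days) reaches it, and the five days between are free: 2^5 = 32. Day 126 is positive in 16 of these, which are also indeterminate; the other 16 are persistent only.
- Day 147 positive and day 21 negative: 2^5 = 32. One has day 147 alone and 16 have day 126 positive, so 17 are indeterminate only. The remaining 15 have an earlier positive but a negative day 126, and meet no class.

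Total: 63 + 16 + 16 + 17 + 15 = 127.

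**Step 3. Five on-treatment samples plus the 90-day sample**

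Samples fall on days 21, 42, 63, 84, 105 and 195, giving 63 patterns.

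- Day 195 negative: 2^5 − 1 = 31, all transient only.
- Persistent needs day 195 and a positive by day 63 (195 − 63 = 132, but 195 − 84 = 111): 7 × 4 = 28. Day 105 is positive in 14, which are also indeterminate; 14 are persistent only.
- Of the other four patterns, three are indeterminate only. One (days 84 and 195 positive, day 105 negative, span 111 days) meets no class.

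Total: 31 + 14 + 14 + 3 + 1 = 63.

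**Step 4. REGN2810**

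On treatment to Cycle 8 (days 21, 84, 147) there are seven patterns: 3 transient, 2 indeterminate, 1 persistent only, 1 both. With last dose at Cycle 10 plus the 90-day sample there are 15: 5 transient, 1 indeterminate, 9 persistent and no overlap. No unclassified pattern appeared on the REGN2810 schedules enumerated (last dose Cycle 8 to 11); three consecutive samples 63 days apart already span 126 days.

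**Step 5. Last sample negative**

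Both indeterminate limbs fail. A single positive is transient; two or more positives are transient below 112 days and persistent from 112 days. Every such pattern falls in exactly one class.

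**The case against.** Four objections deserve an answer.

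*Follow-up resolves it.* Sampling is meant to continue until negative, and by Step 5 the classes then work. In Step 3, all 14 overlaps and the unclassified pattern end on a positive day-195 sample, so another sample would be due; one negative result would put each in a single class. This stands as a limit. It does not remove the defect, because sampling can end on a positive result through cut-off, death, withdrawal or treatment still under way. Treatment may last 2 years, while the study cut-off may fall 12 months after the last patient starts.

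*REGN2810 gaps.* A reader might infer that no planned gap for either drug reaches 16 weeks. Step 1 shows otherwise: the universal overlap holds for isatuximab on schedule, not for REGN2810 at the 90-day sample.

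*Direction.* A reader might infer that persistent ADA will be understated. That follows only if code tests indeterminate first. The SAP states no such order, and a programmer could equally assign persistent first.

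*Size.* Protocol 4.4.2.1 reports isatuximab ADA in 12 of 285 patients in other studies. If that rate applied to all 134 planned Phase 2 patients, 134 × 12/285 ≈ 6 would be positive, and fewer would be classifiable because later-enrolled NSCLC Stage 1 patients give no ADA samples. No REGN2810 rate is given. SAP 2.4.6.7 also lists each sample's status and date, so patients could be reclassified from the report. This supports low severity, not leaving the rule as it is.

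**Conclusion.** The definitions are neither exclusive nor complete when the last sample is positive. On schedule, every persistent isatuximab responder positive at the last two samples is also indeterminate. For REGN2810 the overlap occurs on treatment and, depending on the last cycle given, at the 90-day sample. Induced patients whose positives span under 16 weeks, with the last sample positive and the one before it negative, have no class.

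The pattern counts show that the rules fail; they do not estimate how many patients are affected. They assume samples taken on schedule, with none missed or inconclusive, and both drugs stopped together. The effect is confined to a descriptive table whose classes may not sum to the induced total, and the direction of any misclassification depends on the tie-break chosen. ADA incidence, ADA prevalence and the primary endpoint are untouched. The exclusion of boosted responses is explicit and is not part of the defect. Severity is low.

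**What to change.** Replace the second limb of indeterminate in SAP 2.1.4.8 with: *treatment-induced ADA at two or more time points, first and last ADA-positive samples separated by less than 16 weeks, and the last sampling time point ADA-positive*.

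Add: *in all three classes, the last sampling time point is the last sample with a positive or negative result; inconclusive samples are ignored*. Without this, two positives under 16 weeks apart followed by an inconclusive last sample would still have no class.

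A span of 16 weeks or more is then persistent; anything shorter, including a single positive, is transient if the last sample is negative and indeterminate if it is positive. The 127 patterns in Step 2 become 63 transient, 32 persistent and 17 + 15 = 32 indeterminate. The 63 in Step 3 become 31, 28 and 3 + 1 = 4. None overlaps and none is left out.

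The cost is one or two SAP sentences and the matching derivation code, with no new data. It is best settled before database lock, so that the tie-break is not chosen with results in view.

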2.1.5 Pharmacokinetic variables

The PK sampling times for isatuximab and REGN2810 were provided in the PK/PD flowchart in Section 1.5 of the protocol.

The following PK parameters (listed in [Table 3](#)) will be calculated with PKDMS software (Pharsight) V3.0, using non-compartmental method from isatuximab and REGN2810 concentrations after the first administration on Cycle 1. The parameters will include, but may not be limited to the following:

Table 3 - List of pharmacokinetic parameters and definitions

Parameters	Analyte		Definition
	REGN2810	Isatuximab	
C _{eo1}	X	X	Concentration observed at the end of intravenous (IV) infusion
C _{max}	X	X	Maximum concentration observed
t _{max}	X	X	Time to reach C _{max}
C _{last}	X	X	Last concentration observed above the lower limit of quantification
t _{last}	X	X	Time of C _{last}
AUC _{0-21d}	X		Area under the concentration versus time curve calculated using the trapezoidal method over the dosing interval (21 days)
AUC _{0-7d} or AUC _{0-21d}		X	Area under the plasma concentration versus time curve calculated using the trapezoidal method over the dosing interval (7 days, and for cohorts C and D: 21 days)

C_{trough} are defined as sample collected just before treatment administration during repeated dosing.

In addition, populations PK approaches may be used for both compounds and PK estimates may be used to conduct exploratory exposure-response analyses for safety and efficacy and PK/PD analyses for relevant biomarkers. If done, the data generated will be reported in stand-alone report(s).

2.1.6 Biomarker endpoints

2.1.6.1 Immune Genetic Determinants

Germline genetic data of Fc gamma receptor (FCGR) genes will be analyzed on blood samples collected on Day 1 of Cycle 1:

- FCGR polymorphisms (FCGR3A): For each gene, the results will be of the form AA, Aa or aa with A and a-alleles, the major and minor allele, respectively

2.1.6.2 Immune phenotyping

Immune phenotyping in peripheral blood (baseline, D1 of Cycle 1, 2, 3, 5, 7, 9, end of treatment (EOT) and FUP60) will be assessed. Immune cell sub-populations will be determined by multiparametric flow cytometry based on the expression of different cell surface markers. Percentages of a given immune cell sub-populations and absolute counts as well as expression intensity of certain markers will be provided.

2.1.6.3 PD-L1 expression singleplex IHC

PD-L1 expression on tumor and immune cells will be assessed using tumor tissue (freshly collected tumor biopsy or archival tissue) biopsy at Screening/Baseline and (unless clinically unfeasible) at C2D1.

2.1.6.4 Cluster of differentiation 38 (CD38) expression singleplex IHC

CD38 expression on tumor and immune cells will be assessed using tumor tissue (freshly collected tumor biopsy or archival tissue) biopsy at Screening/Baseline and (unless clinically unfeasible) at C2D1.

2.1.6.5 Immune cell subpopulation tumor infiltration and markers co-expression multiplex immunofluorescence

Immune cell subpopulation tumor infiltration and markers co-expression on different cell sub-populations will be assessed on tumor tissue (freshly collected tumor biopsy or archival tissue) biopsy at Screening/Baseline and (unless clinically unfeasible) at C2D1. Cell sub-populations will be determined by multiplex Immunofluorescence based on the expression of 12 different cell markers. The results will be provided per region of interest (ROI) and the number of cell sub-populations will be provided for 3 regions (total, within tumor, outside tumor).

Per cell sub-population, an average of the results provided per ROI will be calculated for the totality of tumor tissue.

2.1.7 Further therapy after discontinuation of investigational medicinal product administration during the study

Further therapies after discontinuation of study treatment will be collected on a specific eCRF page. The following information will be collected: drug/medication (brand or generic name), start date and end date (if available)/ongoing (otherwise).

2.2 DISPOSITION OF PATIENTS

Patient disposition will be summarized by cohort based on the analysis population defined in [Section 2.3](#).

Screened patients are defined as any patients who signed the study informed consent.

Enrolled patients are screened patients who are planned to receive the study treatment, ie, for whom the investigator ticked “Yes” to the question “Will the patient continue into the study?” at the end of the screening period.

Randomized patients include all patients in cohort A-1 stage 2 and cohort A-2 who signed the study informed consent and were randomized regardless of whether the patient was treated or not.

For patient study status, the total number of patients for each of the following categories will be presented in the clinical study report using a flow-chart diagram or a summary table:

- Screened patients
- Enrolled/randomized patients
- Enrolled/randomized and not treated patients
- Enrolled/randomized and treated patients
- Patients still on treatment
- Patients completed treatment
- Patients who discontinued the study treatments period and reasons for permanent discontinuation

The number and percentage of patients in analysis population (defined in [Section 2.3](#)) will be provided in a summary table.

A summary of the reasons for definitive and premature treatment discontinuation for either treatment will be provided. Definitive treatment discontinuation is defined as the discontinuation of all the study treatments. Premature treatment discontinuation (only for cohorts with the combination therapy) is defined as the discontinuation of one of the study treatments but the other one continued. Listing of the reasons for treatment discontinuation will be provided.

The number (%) of patients treated by country and center will be summarized using the all-treated population (defined in [Section 2.3](#)).

All critical or major deviations potentially impacting efficacy and safety analyses will be summarized by cohort separately. Critical or major protocol deviations will be listed.

2.2.1 Randomization and drug dispensing irregularities

For patients with mCRPC, if an isatuximab monotherapy cohort is initiated, patients with mCRPC will be randomly assigned in a 1:1 randomization ratio to enter Cohort A-1, isatuximab and REGN2810 combination (Phase 2 Stage 2) or Cohort A-2, isatuximab monotherapy (Phase 2 Stage 1).

All randomization and drug-dispensing irregularities will be documented in the clinical study report. The irregularities will be categorized and summarized among randomized patients (number and percentages).

2.3 ANALYSIS POPULATIONS

2.3.1 All-treated population

For both Phase 1 and Phase 2 parts of the study, the all-treated population will include all patients who signed the study informed consent and received at least 1 dose (even incomplete) of the study treatments, either isatuximab or REGN2810.

This population is the primary population for the analyses of efficacy and safety parameters except for DLT evaluation. All analyses using this population will be based on the dose level actually received in the first cycle.

